5.1.4.3 SCREEN FAILURES

Screen failures are defined as participants who consent to participate in the clinical trial but do not meet the inclusion criteria. Specifically, people that register and complete the intake procedures but do not have a medical history or diagnosis of cancer will be considered a screen failure. A minimal set of screen failure information is required to ensure transparent reporting of study results, including to meet publishing requirements and potentially to respond to queries from regulatory authorities. Minimal information includes registration and patient intake information, medical information abstraction and review, demography, eligibility criteria and screen failure details, and any serious adverse event (SAE) or outcome information.

Individuals who do not meet the criteria for participation in this trial (screen failure) for example due to a lack of a cancer diagnosis may be rescreened and may enroll in the XCELSIOR registry later if they meet the entry criteria. Rescreened participants will be assigned the same participant number as for the initial screening.

5.2 VIRTUAL TUMOR BOARD OPERATIONS

5.2.1 VIRTUAL TUMOR BOARD OVERVIEW

XCures acting alone or on behalf of a partner or collaborator will support activities by using a "Virtual Tumor Board" or "VTB". The operations of the VTB are in many respects analogous to the tumor boards run at major cancer centers or molecular tumor boards described in section 2.2.2. The processes outlined in this study protocol describing the VTB are information, as the function of the VTB is to provide individual information services to patients and their physicians. However, research will be conducted on the decision-making process to understand the rationale underlying VTB recommendations in relation to the tracking of patient outcomes within XCELSIOR. Information derived from research on treatment rationales will be available to the VTB to facilitate treatment option identification and associated outcomes as part of the overall learning process.

5.2.2 VIRTUAL TUMOR BOARD PROCESS

Following registration and consent, XCures acting alone or on behalf of a partner or collaborator will contact the patient to begin collection and abstraction of their medical information into a patient summary to be provided to the VTB. This process includes identification of similar patients medically-logical treatment options, including clinical trials, that have been suggested by the VTB for similar patients or have otherwise been identified as medically logical for similar patients, with relevant information from the study Leaderboard, if available. The

completed summary is then submitted to at least three VTB members selected based on their availability and expertise for review. The VTB using will review the case, options, and discuss using on- or off-line technology support, to reduce the options into a list of best options at clinical equipoise. Rationale capture for addition, inclusion, or removal is collected for global learning analysis. Additional rounds of review and discussion may be undertaken to further refine the option list and VTB members may request additional information, including review of source records, to support their review. Once the option set is reduced the patient utility is applied and simulation analysis is run to assess the global information gain value of the options in the equipoise set. Together these are provided to the VTB to determine whether they then wish to update their selection of options. Finally, the refined option list, with supporting information and rationales, plus information gain value and alignment with patient preference are provided to the patient and their doctor for consideration.

5.2.4 QUALIFICATION AND SELECTION OF VTB MEMBERS

Virtual Tumor Board members are independent experts that work with XCures acting alone or on behalf of a partner or collaborator to provide review and assessment of patient cases. Members are selected based on clinical and academic expertise in the treatment and study of specific tumor types. Members of the VTB will include appropriately qualified individuals representing clinician disciplines, including medical, surgical, or radiation oncologists, as well as pathologists and/or radiologists; pharmacologists; molecular, cancer or systems biologists; and others, as needed to fulfil the VTB function. Members should be free of conflicts of interest in accordance with the policies described herein and in compliance with applicable regulations.

5.2.5 VTB FINANCIAL DISCLOSURE AND CONFLICT OF INTEREST POLICY

VTB members of should be free of conflict of interest and measures will be implemented to minimize perceived conflict of interest. Specifically, the VTB will operate under the rules of an approved charter or SOP, and discussions will be documented and archived for future analysis. VTB members should disclose to XCures acting alone or on behalf of a partner or collaborator real or perceived conflicts-of-interest, which will be documented at the time of their appointment. VTB members should refrain from reviewing cases for which they believe they have a conflict-of-interest. Members will serve a two-year term of service, which may be renewed indefinitely. Upon renewal of service, VTB members will update their disclosures and from time-to-time as necessary for the

publication of findings in which they have been named as an author. VTB members should comply with their institutional and other state and local conflict-of-interest laws, regulations, or policies. XCures acting alone or on behalf of a partner or collaborator will review disclosures against public information maintained by the Centers for Medicare and Medicaid Services (CMS) in the OpenPaymentsData on-line database and search engine.

5.2.6 RELATION TO VDMC

Members of the VTB may participate in the vDMC, the purpose of which is to review the overall data generated in XCELSIOR and identify insights for dissemination.

5.2.7 AUTHORSHIP AND PUBLICATION COMMITTEE

VTB members that are involved in the review of patient cases may be named as authors on publications which result from analysis of those cases. Other personnel involved with the collection, management, analysis, or interpretation of data will be named as authors either individually or in the form of group authorship with their contributions identified in accordance with ICMJE policy.

The VTB and vDMC may assemble ad hoc publication committees to author posters or publications on specific topics as data from the registry generates meaningful information. XCures, as the sponsor, will have overall responsibility for the management, analysis, interpretation, and publication of the data. Therefore, Cancer Commons will appoint representatives to serve on all publication committees to ensure that the perspectives of patients and advocates are incorporated in the dissemination of information and retains ultimate authority over these activities.

6 PATIENT ACCESS SUPPORT CORE

The purpose of the Patient Access Core is to provide support and assistance to ensure that access to medicallylogical options suggested by the VTB are available for patients.

There are many barriers to access facing late-stage cancer patients and for these patients especially, time is of the essence. These barriers can be administrative, logistical, geographic and financial. However, patients are the most valuable resource in precision oncology. Barriers to access not only cost lives but the prevent essential learning that will help other patients. Thus, a continuously-learning model for precision oncology must ensure that patients receive medically-logical treatments and that the results of that treatment are captured for learning purposes.

To overcome these barriers, XCures acting alone or on behalf of a partner or collaborator will attempt to create a clearinghouse for patients trying to access therapies either through clinical trials or through expanded access programs. This clearinghouse would facilitate the matching of targeted anti-cancer therapies made available in clinical trials or under compassionate use to patients and their doctors. This type of central player is absent in the compassionate use arena, leading to the many challenges matching patients to trials. Although there are firms doing trial matching with varying degrees of success, there are many more barriers that must be overcome. For example, after matching patients to potential trials, patients must be transferred to sites for screening, which isn't typically covered by sponsors or insurers. This, ensuring financial support for travel is required—medical bills, and in particular, cancer treatment is a leading cause of personal bankruptcy in America (Murphy, 2018).

The patient access core can provide liquidity by helping to match patients to trials and prevent failures by stepping in when patient can't access a trial to assist with getting them a medically-logical therapy and collecting the data in a registry. That data may prove of use later both directly and indirectly to patients or sponsors. Conversely, sponsors may be unwilling to risk trials for certain patients due to fear of failure but could provide single patient drugs under compassionate use terms, which can immediately help patients and build evidence to support larger trials later.

Similarly, XCures acting alone or on behalf of a partner or collaborator with XCELSIOR can facilitate pay-forresults between insurers and sponsors in cases where a patient may benefit from the off-label use of a drug, but a payor is unwilling to cover the drug without evidence of medical necessity. In such cases, XCELSIOR can work with willing sponsors to provide a bridge of drug access to a time point in where evidence of drug effect can be assessed and provided as support. During that time, negotiations with an insurer can take place, but the patient does not have to defer treatment. Similarly, private oncology practices sometimes end up taking on this risk, by procuring and administering treatment under the hope that the insurer will agree to compensate them at a later date. This arrangement is becoming less common as the costs of treatments increase. However, this type of pay-for-results market-making can be of benefit to patients, insurers, and manufactures at the same time.

These activities represent a service, however information collected or generated in the process of providing access services may be used as part of research and publication efforts. For example, Sireci and colleagues (2017) reported on the rate of insurance reimbursement received for patients receiving an off-label targeted

cancer therapy identified by their organizational molecular tumor board. The information collected to support patient access services are Services Data rather than Research Data, but specific information about Services provided to patients participating in XCELSIOR and associated Services Data may be abstracted into the Research Database where such information becomes part of the specified Research Data elements. For example, if travel funds were provided to a registry participant to facilitate enrollment in an externally-sponsored clinical trial, information about the patient's participation in that trial will be collected.

6.1 TREATMENT ACCESS SUPPORT

Acting on behalf of Cancer Commons or other partners and collaborators, xCures may receive commercially available drugs directly from sponsors/manufacturers for the purposes of providing expedient treatment access services to patients. XCures acting alone or on behalf of a partner or collaborator many negotiate directly with sponsors to provide a supply of approved drugs to be stored at a central pharmacy provider, which may then provide matched therapies to sites designated for administration to specific patients participating in XCELSIOR. This process is envisioned in two primary ways. First, sponsors may provide drugs for patients eitheras bridging therapy, enabling patients to start treatment rapidly without concerns about payment while XCures acting alone or on behalf of a partner or collaborator works with patients' physicians to secure insurance coverage due to medical necessity. It is expected that within two months of bridging therapy, information related response through clinical, imaging, or laboratory testing would be developed and form the basis of support for effectiveness in a specific patient. This information would support insurance coverage without delaying the start of treatment. In addition, analytic methods may be incorporated to demonstrate effectiveness in similar patients based. Second, sponsors may provide drug directly out of altruism, in which case the donation may be a charitable contribution to a 501(c)3 entity, or in exchange for access to de-identified data that improves their understanding about which patient characteristics correlate with effectiveness. In addition, XCures acting alone or on behalf of a partner or collaborator will attempt to help patients enroll in co-payment support programs and may raise a charitable fund to help patients with insurance cover co-payments when external copayment support is unavailable.

For patients that are matched to clinical trials, XCures acting alone or on behalf of a partner or collaborator may notify sponsors in cases where a patient faces a logistical, geographic, or financial barrier preventing them from traveling to a clinical trial site. In those cases, XCures acting alone or on behalf of a partner or collaborator may work with the sponsor to provide travel support, open a clinical trial site for the patient that is more convenient, or if the treatment is medically logical, but a clinical trial isn't possible, to work with the sponsor and patient's oncologist to provide the treatment under compassionate use.

Treatment Access Support Services are services provided to patients by XCures acting alone or on behalf of a partner or collaborator or their designee, agent or affiliate to further their mission of making treatment options available to patients and their doctors. Services activities are considered distinct from research activities, but information about Services provided by XCures acting alone or on behalf of a partner or collaborator may be abstracted into the Research Dataset if those activities include information pertinent to the registry, such as the name or dose of an anti-cancer treatment provided to a patient's physician for administration on a compassionate use basis. In the event that provision of access to therapies involves investigational treatments,

such treatments will be administered by the patient's physician under and approved IND and study protocol specific for the use of such treatments that is distinct from the XCELSIOR data registry.

6.2 PATIENT ACCESS SUPPORT SCHEMA

Access Support Process

7 PATIENTS OUTCOMES CORE

7.1 DATA HANDLING AND RECORD KEEPING

7.1.1 DATA MANAGEMENT

A registry database will be maintained with identified registry data elements captured into the REDCap Cloud EDC system, a commercial eClinical Platform that is 21 CFR Part 11 Validated, HIPAA & FISMA compliant, and WHODrug and MedDRA certified. The system All access and activity in the system is tracked and can easily be monitored by the Administrator. The system has a login audit feature that tracks who has logged into the system, the date and time of login, and the IP address of the connection. The system also tracks failed logins and automatically locks a user's account after several failed attempts. The REDCap Cloud system has a robust audit trail that shows all changes to any records within the system including who made the change, the date and time of the change, the field that was changed, the old value of the field and the new value of the field. Access can be monitored via a dashboard or email alerts. Data management activities will follow standard operating procedures.

7.1.2 STUDY RECORDS RETENTION

Study data including source records and case reports forms will be maintained in electronic format indefinitely, but at a minimum until two years after the last participant is deceased. De-identified databases derived from the study records may be made available to other researchers in the future and may be retained by those organizations indefinitely based on the terms of the agreement under which the data was provided.

7.1.3 SOURCE DOCUMENTS

Source data can include clinical findings and observations, or other information incorporated into the registry database to support analysis of outcomes, effectiveness, and safety aims. Source data is all information from which information in the registry database is derived in original form (or certified copies of an original record). Examples of these original documents and records include but are not limited to the following: electronic medical records, clinical and office charts, laboratory notes, memoranda, correspondence, subjects' diaries or patient-reported questionnaires, data from automated instruments, such as ECG machines, photographs and other imaging (DICOM) files, slides, pharmacy records, and the reports documenting medical interpretation of those files.

Data may be entered into the eCRF either manually by a study team member performing data abstraction from the EMR or electronically using direct entry of data into the or from an electronic import of data. Patients may also enter information directly into the eCRF using a patient-facing survey functionality either over the Web or using a smartphone app. Data elements originating in EMR may be automatically transmitted directly into the eCRF using a suitable API. Source data derived in that manner may have an intervening process, such as abstraction by third-party (e.g., Ciitizen) software including processing using machine learning algorithms prior to transferring to the eCRF. XCures acting alone or on behalf of a partner or collaborator will retain source records in a secure that will be maintained separately and securely from the eCRF. However, metadata tagging may be employed to electronically map source data back from the eCRF to the source data record to create an audit trail.

Upon registering for XCELSIOR at the Web site, patients under their right-of-access to their medical records may authorize XCures acting alone or on behalf of a partner or collaborator to receive any and all historic medical records available, as necessary to assess and evaluate their case history and generate recommendations through the VTB process.

7.1.4 DATA ELEMENTS FOR COLLECTION

- 1. Demographics (e.g., name, date of birth, gender, ethnicity, race, contact information, name relationship and contact information for legally-authorized representative.
- 2. Medical Record Information (e.g., MRN, Primary Hospital, Hospital Address, Primary Doctor, Contact email, Contract number)
- 3. Diagnostic and Clinical Information (histopathology, imaging, symptoms, DRG, clinical examination results)
- 4. Laboratory Information (clinical labs, cytogenetic, molecular, NGS or other test results)
- 5. Anti-cancer Therapy (Radiotherapy, Adjuvant/Neoadjuvant therapy, Chemotherapy, Surgical treatment, Device treatments, supportive care, dietary or lifestyle interventions)
- 6. Safety and Tolerability (side-effects, hospitalization, AE, SAE)
- 7. Outcomes (Functional, Performance, Quality-of-life, Response measures, mortality)

Specific measures will be incorporated that are appropriate for the tumor type or disease under study. For example

7.2 ANTI-CANCER AND OTHER THERAPIES OR TREATMENTS

For this registry information about anti-cancer treatments and related, supportive care, as well as treatment administered in response to CTCAE grade 3 or more severe adverse events will be abstracted from the medical record and stored within the CRF. In cases where an anti-cancer treatment is not considered a prescription treatment (e.g., use is not restricted to prescription only by a properly authorized/licensed clinician) such treatments will be collected to the extent possible using information in the records or provide by the patient or their physician. Examples include patient-reported regimens that include vitamins, supplements, herbal or complementary or alternative medicines taken explicitly for anti-cancer or supportive care purposes.

7.2.1 TREATMENT SWITCHING

Since the purpose of this study is to develop information that supports personalized medicine in oncology, patients and their clinicians may switch or modify treatments in response to clinical outcomes. Treatment switching will be collected and mark an event for outcomes assessment purposes. The cause of treatment switching will be identified via discussion with the patient and their physician in order to code the reason for switching such as side-effects or lack of efficacy. The reason for treatment discontinuation or switching will be

recorded in the eCRF. Patients that switch treatments may request that their case be reassessed through the VTB process.

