Randomization and blinding, while helpful for certain aspects of clinical trial validity in n-of-1 designs are not required for the aggregation or meta-analysis of data and statistical inference thereof, nor are they essential for making inferences about the effectiveness of cancer treatments. As noted in the FDA Guidance on Clinical Trial Endpoints for the Approval of Cancer Treatments, Objective Response Rate and Complete Response can both serve as approvable endpoints in single-arm, open-label cancer studies. Within the XCELSIOR study framework, use of internal controls, such as prespecified estimates for patient trajectory based on individual characteristics, for example TTP ratio, as investigated by Mick and colleagues using paired TTP analyzed as a hazard ratio (Mick

et al., 2016), enable a prospective evaluation of effectiveness with each patient as their own control, the result of which can be aggregated using Bayesian or other meta-analytic methods. This approach is especially powerful in rare diseases (Abrahamyan et al., 2014), which is a useful model for precision oncology, in which NGS data with other baseline covariates places each patient into at most, a very small cluster of similar patients. Those authors further highlight the importance of looking for large effect sizes in rare diseases, which is a key aspect of signal detection in precision medicine generally and XCELSIOR specifically.

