7.3 DISCONTINUATION OF PARTICIPATION

Discontinuation of treatments does not mean discontinuation from the study, and patients in XCELSIOR have the option of returning their case to the VTB process for new or additional options development if they experience side-effects or progress on a chosen therapy. Furthermore, for late-stage cancer patients, hospice is considered a likely option during the study. Patients are not considered discontinued or withdrawn from the study if they choose to receive hospice care. Patient information will be collected until death, unless the patient chooses to withdraw from the study. Patients are free to withdraw at any time by providing notice of withdrawal in writing using established procedures documented on the xCures Web site and including an option to provide a reason for withdrawal from the study. Withdrawal from the study means that no additional data will be collected on the patient (excluding public records searches to confirm dates of death) and does not constitute revocation of XCures acting alone or on behalf of a partner or collaborator right to use the data collected prior to withdrawal for the purposes described herein.

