7.3.2 LOST TO FOLLOW-UP

As a patient advocate, XCures acting alone or on behalf of a partner or collaborator frequently contacts patients to share information and assist with discussions related to care, coverage, or responses to treatment. If a patient is unreachable, XCures acting alone or on behalf of a partner or collaborator may continue to attempt to contact the participant, their doctor (or other members of their treatment team), or their designated Emergency Contact by phone, email or similar method. Patients that are not reachable will be considered lost to additional follow-up. Patients that choose to receive hospice care, will not be contacted further. In either case, XCures acting alone or on behalf of a partner or designee may undertake public records search

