7.5 Adverse Events and Serious Adverse Events

7.5.1 DEFINITION OF ADVERSE EVENTS (AE)

The XCELSIOR registry is not a treatment protocol, it is a non-interventional registry study. However, to facilitate the generation of real-world evidence for the effectiveness and safety of cancer treatment regimens, information about spontaneously reported adverse events or events identified through the processing of the patient medical or health records will be identified analytically based on the emergence of the event in relation

to its presence or absence in the medical record at prior time points. Events may also be reported directly by the patient or their physician using surveys or directly through correspondence with XCures acting alone or on behalf of a partner or collaborator and/or xCures. In such cases, reasonable efforts will be made to gather information about the event.

Adverse events will mean any untoward medical occurrence associated with the use of an intervention whether or not considered intervention-related (21 CFR 312.32 (a)). Coding of AEs will be based on the CTEP dictionary (https://ctep.cancer.gov/protocolDevelopment/codes_values.htm#disease)and the severity of AEs will be graded based on CTCAE (https://ctep.cancer.gov/protocolDevelopment/electronic_applications/ctc.htm). In both cases, reasonable efforts will be made to code the events in accordance with standard dictionaries if the information is available directly or by imputation.

The primary focus of the Research Data will be on treatment-emergent events that meet the CTCAE criteria of Grade 3 or higher, therefore these events will be captured and assessed in the registry database to the extent possible. Assessment and analysis will focus on identifying treatment-emergent adverse events in relation to anti-cancer treatments identified within the patient's medical record, particularly those related to dose modification or interruption of anti-cancer therapies, or other therapeutic intervention or modification, including hospitalization or other medical treatment. Discontinuation of therapy due to lack of efficacy will be treated as a therapeutic outcome not an Adverse Event.

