8.1.4 ANALYTIC SIGNAL DETECTION

General and disease-specific response signals will be detected using traditional query detection methods augmented with both human expertise and machine learning techniques. Signals will be detected by monitoring routine and spontaneous assessments collected from the medical record and augmented with surveys, which may include labs, imaging, patient- and physician-reported questionnaires, and other information such as treatment switching or progression declarations. Signals may be detected from changes in magnitude or rate of change and scored based on direction of the change and correlation with the VTB treatment rationale. Once detected, potential signals will be escalated for human review by a scientist, medical director, or the VTB/vDMC. Signals may be mapped to response criteria, for example RANO. Spontaneous response measures, such as time-to-progression, time-to-treatment switching, and/or changes to anti-cancer therapy regimen will be detected and scored using paired TTP or TTTS and in relation to baseline forecasts.

It should be noted that signal detection in non-linear networked systems, such as the composite responder analysis integrating numerous non-linear assessments into a network of aggregated n-of-1 experiments, benefits from a certain level of "noise" within the network. This phenomenon is called stochastic resonance and is widely used in telecommunications and other networked systems to amplify weak signals in a noisy environment. Such approaches may be considered for enhancing signal detection in XCELSIOR.

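### Does the paired time-to-switch measure favour the newer line because lines ending in hospice or death are not named as events?

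*Protocol*

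**What the plan says.** Section 7.2.1: "Treatment switching will be collected and mark an event for outcomes assessment purposes". It adds that the reason for stopping or switching is entered in the eCRF.

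Section 8.1.4 lists time-to-progression with "time-to-treatment switching, and/or changes to anti-cancer therapy regimen will be detected and scored using paired TTP or TTTS and in relation to baseline forecasts". Section 3 allows time-to-switching and TTP ratios where appropriate, next to durable response judged against historical controls or prospective forecasts.

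Section 2.2.9 says that internal controls, with forecast trajectories and the TTP ratio as examples, "enable a prospective evaluation of effectiveness with each patient as their own control".

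On how a line may end, section 7.5.1 says "Discontinuation of therapy due to lack of efficacy will be treated as a therapeutic outcome not an Adverse Event". Section 7.1.4 lists mortality among the outcomes to be collected, and the synopsis lists TTF, PFS and OS as possible endpoints.

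On follow-up, section 7.3 says "for late-stage cancer patients, hospice is considered a likely option during the study", keeps such patients in the study, and states "Patient information will be collected until death, unless the patient chooses to withdraw from the study". Section 7.3.2 says "Patients that choose to receive hospice care, will not be contacted further" and then, for hospice patients and unreachable patients alike, "In either case, XCures acting alone or on behalf of a partner or designee may undertake public records search". Section 4.3 runs the study until the last patient's date of death is confirmed.

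**The concern.** A pair needs two lines, so the earlier line always led to a further treatment. The later line may instead end in hospice or death. Section 2.4.1.1 expects only two or three treatment options per patient and section 7.3 expects hospice, so terminal endings could be common.

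If only a switch counted and terminal endings were censored, failures would be removed from the newer line but never from the older one. An inert drug would then look better than its predecessor. Efficacy signals feed the Leaderboard (8.1.2) and the vDMC's decisions on treatment options (7.4), so optimism of this kind would matter even in a registry without formal hypotheses.

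The follow-up text seems to make it worse. Contact stops at hospice and the death search is optional, so a later analysis plan might lack the dates it needs.

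**Working it through.** The protocol gives no figure to reproduce: section 8.1.5 states no sample size, and no ratio threshold is adopted. The check has three steps.

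**1. Is a biased rule stated?**

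- 7.2.1 makes a switch an event. It does not make it the only one.
- 7.2.1 also records reasons for stopping, 7.5.1 treats stopping for lack of efficacy as a therapeutic outcome, and 7.1.4 collects mortality.
- 8.1.4 scores progression and regimen changes as well as switching, and also compares with baseline forecasts.
- No section says that a line ending in hospice or death is censored or dropped.
- The TTP ratio named in the own-control text of 2.2.9 has progression as its event, so the asymmetry applies fully to TTTS and less to TTP.

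**2. Would one rule be plainly right?**

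Assumptions: an inert drug; exponential times with median 4.0 months on both lines; a share q of lines ending terminally, set at 10, 20 and 30%. None of these values is in the protocol. Results are ratios of medians, newer over prior line.

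*Terminal ending unrelated to time.* Selecting prior lines that were not terminal leaves their median at 4.0 months.

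- Censored: the switching hazard falls by the factor (1 − q), so the ratio is 1/(1 − q) = 1/0.9, 1/0.8, 1/0.7 = 1.11, 1.25, 1.43.
- Dropped: 1.00 at each q.
- Counted as failure: 1.00 at each q.

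*Failures before the median twice as likely to be terminal.* The terminal probability is 4q/3 before the median and 2q/3 after it, which averages to q. Among non-terminal lines the median is multiplied by

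f = 1 + log2[(1 − 2q/3)/(1 − q)]

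- q = 0.10: 1 + log2(0.9333/0.9) = 1.052
- q = 0.20: 1 + log2(0.8667/0.8) = 1.115
- q = 0.30: 1 + log2(0.8/0.7) = 1.193

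These look like an upward bias from dropping terminal pairs, but only if the prior line is left unselected with median 4.0. By the concern's own premise the prior line was non-terminal, so under the same process its median is also multiplied by f:

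- Dropped: f/f = 1.00 at each q.
- Counted as failure on the newer line: 1/f = 0.95, 0.90, 0.84.
- Censored: the newer line's median is multiplied by 1 + (4q/3)/(1 − 2q/3) = 1.143, 1.308, 1.500. Divided by f, this gives 1.09, 1.17, 1.26.

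| Rule for terminal endings | Unrelated to time, q = 10/20/30% | Early failures more often terminal, q = 10/20/30% |
|---|---|---|
| Censored | 1.11 / 1.25 / 1.43 | 1.09 / 1.17 / 1.26 |
| Dropped | 1.00 / 1.00 / 1.00 | 1.00 / 1.00 / 1.00 |
| Counted as failure | 1.00 / 1.00 / 1.00 | 0.95 / 0.90 / 0.84 |

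A simulation of 2,000,000 pairs before selection agrees with the closed forms to within 0.01. Counting hospice and death as failure is thus unbiased in one setting and biased against the newer line in the other. Applying it to both lines changes nothing, because a prior line that belongs to a pair cannot have ended in death.

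**3. Do the follow-up sections conflict?**

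- 7.3.2 ends contact with hospice patients; it does not end data collection.
- 7.3 keeps them in the study and collects information until death. 7.1.3 provides for medical records obtained under the patient's right of access, which is a route other than contact.
- 4.3 already requires confirmed death dates.
- The choice of hospice must be known before contact can stop. If hospice entry ended the line, the later death date would not be needed for the paired measure.

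**The case for a change.** The strongest opposing case is that the protocol, not the analysis plan, gives a switch its event status, and that an analysis plan cannot recover dates that were never collected. The paired measure also stands in for a comparator, in patients for whom terminal endings are likely.

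Parts of this stand. No section states how a terminal line enters paired TTTS. Censoring such lines would favour the newer line in both settings above. The optional death search is weaker than section 4.3 requires, chiefly for unreachable patients.

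The rest does not carry the concern. The protocol does not adopt the censoring rule on which the inflation depends. Deciding whether death or hospice is an event, a censoring time or an exclusion in a derived time-to-event measure is ordinary analysis-plan content, so silence here is no error. The data for that decision are planned: reasons for stopping, mortality, and record collection until death. The permissive verb in 7.3.2 is loose beside 7.3 and 4.3, but the three sections can all be followed together.

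**Conclusion.** The concern does not hold. The protocol names a switch as one event, collects what is needed to treat other endings as events, and states no rule that biases the paired measure. The possible inflation of 1.11 to 1.43 rests on an assumed terminal share of 10 to 30%, exponential times, terminal endings unrelated to time, and a censoring rule found nowhere in the document. Counting hospice and death as failure is not a neutral repair: it gives 0.95 to 0.84 when early failures are twice as likely to be terminal and the prior line is selected as non-terminal. The choice is a trade-off for the analysis plan, and no change to the protocol is needed on this point.
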